### **10.2 Population pharmacokinetics and exposure response**

Population pharmacokinetics and exposure-response modeling are not in the scope of the SAP and will be described in separate data analysis plans.

## **11 OTHER ANALYSES**

Data of Bayley Scales of Infant and Toddler Development®, Third Edition (Bayley-III) and Columbia Suicide Severity Rating Scale will only be listed. The analysis of the Bayley-III scales data will be performed in the follow-up study, SP848.

---

## 13 APPENDICES

### 13.1 Significant Adverse Events

**Table 13-1: List of other significant AEs**

MedDRA Preferred Term
HEPATOTOXICITY RELATED TERMS
Hepatitis toxic
Hepatotoxicity
Drug-induced liver injury
Liver function test abnormal
Alanine aminotransferase increased
Aspartate aminotransferase increased
CARDIAC AND ECG RELATED TERMS
Atrioventricular block complete
Atrioventricular block second degree
Bradyarrhythmia*
Bradycardia*
Cardiac pacemaker insertion
Atrial fibrillation
Atrial flutter
Sinus bradycardia*
Ventricular tachycardia
Ventricular fibrillation
Heart Rate decreased*
Sick sinus syndrome
SUICIDALITY RELATED TERMS
Completed suicide
Depression suicidal
Suicidal behaviour
Suicidal ideation
Suicide attempt
Intentional self-injury
Self injurious behaviour

**Table 13-1: List of other significant AEs**

MedDRA Preferred Term
Self-injurious ideation
Intentional overdose
Poisoning deliberate
ADDITIONAL TERMS
Loss of consciousness
Syncope

\* All cases with reported reduced heart rate will be reviewed and only cases with marked bradycardia (marked reduction in heart rate) with HR <45 bpm will be listed as 'Other Significant AEs'.

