5.1.2 Planned number of subjects and site(s)

Approximately 50 subjects will be enrolled. It is planned to enroll approximately 40 subjects between 4 years and <18 years of age and at least 10 subjects between 1 month and <4 years of age.

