11.3 Adverse events of special interest

An AE of special interest is any AE that a regulatory authority has mandated be reported on an expedited basis, regardless of the seriousness, expectedness, or relatedness of the AE to the administration of a UCB product/compound.

The following are LCM AEs of special interest:

- The following arrhythmias: atrial fibrillation/flutter, ventricular tachycardia or fibrillation, AV block (second-degree, Type I and II, and third-degree), and marked bradycardia for subject's age
- Syncope or loss of consciousness (other than seizure-related)
- Serious suspected multiorgan hypersensitivity reactions

Serious suspected multiorgan hypersensitivity cases may be identified and reported to the sponsor by the investigator using the following algorithm as agreed with the USA Food and Drug Administration (FDA):

- An AE or laboratory value (as defined in the following text) suggestive of internal organ involvement (including but not limited to hepatitis, nephritis, pneumonitis, carditis, colitis, encephalitis, pancreatitis, myositis, arthritis, or hematologic system involvement) combined with at least 1 of the following: fever, rash, lymphadenopathy, or eosinophilia.

Treatment-emergent abnormal laboratory value criteria suggestive of internal organ involvement or eosinophilia:

- Eosinophils % $\geq 10\%$
- Eosinophils absolute $\geq 0.5\text{G/L}$
- Neutrophils absolute $< 1.5\text{G/L}$
- Platelets $\leq 100\text{G/L}$

- ALT ≥ 2 x ULN
- AST ≥ 2 x ULN

Adverse events of special interest must be reported in the same way as SAEs (see Section 11.2.2).

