For health care resource use parameters, the following will be evaluated: concomitant AEDs, medical procedures, health care provider consultations not related to study, hospitalizations not related to study. Health care resource use parameters will be collected according to the tabular schedule of study procedures, Section 5.2.

Change #34

Section 11.3 Adverse events of special interest

- The following arrhythmias: atrial fibrillation/flutter, ventricular tachycardia or fibrillation, AV block (second degree, Type I and II, and third degree), and marked bradycardia (<45 beats/min)

Has been changed to:

- The following arrhythmias: atrial fibrillation/flutter, ventricular tachycardia or fibrillation, AV block (second degree, Type I and II, and third degree), and marked bradycardia **for subject's age**

Change #35

Section 11.7.4 Vital signs, body weight and height

Noninvasive BP (systolic and diastolic) and pulse will be measured at clinic visits in a sitting position after at least 3 minutes at rest, according to the tabular schedule of study procedures in Section 5.2. Body weight will be determined without shoes and wearing light clothing, and height will be measured without shoes. Body weight and height will be assessed according to the tabular schedule of study procedures in Section 5.2.

Has been changed to:

Noninvasive BP (systolic and diastolic) **and pulse rate** will be measured at clinic visits **after at least 3 minutes at rest in a supine position**, according to the tabular schedule of study procedures (Section 5.2). **Assessment of orthostatic changes (only in ambulatory subjects) will be as follows: after the 3-minute measurement in supine position, the subject is asked to stand up, and BP and pulse rate are taken at approximately 1 minute**

and 3 minutes after standing up, as feasible. Body weight will be determined without shoes and wearing light clothing, and height will be measured without shoes. Body weight and height will be assessed according to the tabular schedule of study procedures in Section 5.2.

Change #36

Section 11.7.8 Achenbach CBCL

The same scale will be completed at Visit 1, Visit 9 (or the Early Termination Visit) and again by the same parent(s) or legal representative(s) in the open-label study, SP848 (if applicable). The completion of the Achenbach CBCL will require approximately 45 minutes.

Has been changed to:

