### 8.2.2 Adverse events

Treatment-emergent AEs (TEAE) are defined as those events which start on or after the date of first LCM administration and within 30 days following the date of last LCM administration, or whose severity worsens within this time frame.

Other significant AEs are defined in Appendix 13.1 (Table 13-1).

An overall summary of AEs will provide the numbers and percentages of subjects with at least 1 TEAE, serious TEAE, other significant TEAE, TEAE that led to discontinuation, drug-related TEAE, drug-related serious TEAE, severe TEAE, AE leading to death, and TEAE leading to death. The AE overall summary will be repeated by syndrome subgroups (as described in Section 4.8).

The following summaries of AEs will be provided by primary SOC and PT:

- TEAEs
- TEAEs during the Titration Period
- TEAEs during the Maintenance Period
- TEAEs by syndrome subgroups (as described in Section 4.8)
- TEAEs including subject numbers

- Serious TEAEs
- Serious TEAEs including subject numbers
- TEAEs leading to discontinuation
- TEAEs leading to discontinuation including subject numbers
- TEAEs by maximum intensity
- Nonserious TEAEs
- Nonserious TEAEs occurring in > 5% of subjects
- Other significant TEAEs

The following summaries by primary SOC and PT will be presented overall only (ie, not by age group).

- TEAEs by relationship to LCM
- Serious TEAEs by relationship to LCM
- Nonserious TEAEs by relationship to LCM
- Fatal TEAEs by relationship to LCM
- Nonserious TEAEs occurring in at least 5% of subjects by relationship

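### The SAP counts bradycardia events as other significant AEs only below 45 bpm at every age, which conflicts with the protocol's age-relative wording and lies far below the SAP's own low limits for young children

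*SAP*

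**What the plan says.** SAP Section 8.2.2 hands the definition to the appendix: "Other significant AEs are defined in Appendix 13.1 (Table 13-1"). That list feeds two outputs: the other significant TEAE line of the overall AE summary, and a separate table by SOC and PT. Under SAP Section 3.1 both are shown overall and by age group, the youngest group being 1 month to under 4 years.

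Four terms in Table 13-1 are starred: Bradyarrhythmia, Bradycardia, Sinus bradycardia and "Heart Rate decreased". The footnote has all reports of reduced heart rate reviewed, and then "only cases with marked bradycardia (marked reduction in heart rate) with HR <45 bpm will be listed as" other significant AEs. The cut-off is the same at all ages.

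Protocol Section 11.3 includes, among the lacosamide AEs of special interest, "marked bradycardia for subject's age". It gives no rate in bpm. Protocol Section 5.1.2 plans for "at least 10 subjects between 1 month and <4 years of age" among about 50 subjects.

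Elsewhere the SAP does use age-specific low limits: in Table 8-1 (Vital Signs Abnormality Criteria) for markedly abnormal pulse rate, and in Table 8-2 (Electrocardiogram Abnormality Criteria) for ECG heart rate.

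**The concern.** One rate cannot separate marked from unremarkable bradycardia across the range from infancy to late adolescence, and the SAP acknowledges this in its vital-sign and ECG tables. In the AE classification it does not. A bradycardia event in a child under 6 months with a heart rate of 60 bpm is markedly abnormal as a pulse rate under Table 8-1, 40 bpm below the limit, yet is not an other significant AE.

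What is at stake is the reading of one classification in the study report. Arrhythmia is a named special-interest topic for this drug, and the SAP provides no separate table of AEs of special interest, so Table 13-1 is its nearest equivalent. A zero on the bradycardia lines in the youngest age column would largely reflect the filter and would say little about whether such events occurred. An event sent to the sponsor as one of special interest could be missing from that table.

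**Working it through.** The plan gives no figure to reproduce, since 45 bpm is a classification cut-off and not a calculated quantity. The check compares the current texts and measures the distance between the SAP's thresholds.

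**Step 1: current texts side by side.** Protocol 11.3 is relative to age; the SAP Table 13-1 footnote is absolute. SAP Section 2 lists Protocol Amendments 1 to 5 as its basis, and SAP Section 3.9 reports no changes to protocol-defined analyses, so no departure is declared or explained.

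**Step 2: likely origin.** Protocol Section 17.2 (Amendment 1, Change #34) shows that 11.3 formerly read "marked bradycardia (<45 beats/min") and was changed to the age-relative wording. That text is superseded and is not itself an error. It only suggests where the SAP's number came from.

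**Step 3: size of the gap.** Gap = SAP low limit − 45. Ratio = 45 / SAP low limit.

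| Age | Low pulse limit, Table 8-1 | Low ECG heart-rate limit, Table 8-2 | Gap (bpm) | Ratio | Whole-number rates flagged low but not counted |
|---|---|---|---|---|---|
| <6 months | <100 | <100 | 100 − 45 = 55 | 45/100 = 45% | 45 to 99 |
| 6 months to <3 years | <90 | <90 | 90 − 45 = 45 | 45/90 = 50% | 45 to 89 |
| 3 to <12 years | <60 | <60 | 60 − 45 = 15 | 45/60 = 75% | 45 to 59 |
| Older subjects | ≤50 | <50 | 50 − 45 = 5 | 45/50 = 90% | 45 to 50 (Table 8-1) or 45 to 49 (Table 8-2) |

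For older subjects the two tables differ. Table 8-1 uses ≤50 at 12 to under 17 years and, from 17 years, also requires a fall of at least 15 from Baseline. Table 8-2 uses <50, with its last row printed as >12y.

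Below 3 years, an event must therefore have a rate below half the SAP's own low limit to be counted, or below 45% of it under 6 months.

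**Step 4: reach of the filter.** Table 13-1 holds 6 hepatic, 12 cardiac or ECG, 10 suicidality and 2 additional terms: 6 + 12 + 10 + 2 = 30. Four are starred, so 30 − 4 = 26 are unaffected.

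**Step 5: does the review clause help?** No. After review, only cases below 45 bpm are listed. Read literally, an event with no recorded heart rate cannot be shown to meet the condition and drops out too.

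**The case against.** There are four serious arguments against making much of this.

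- **Different lists.** Protocol 11.3 governs expedited reporting. Table 13-1 is the SAP's own list: it adds hepatic and suicidality terms, omits multiorgan hypersensitivity, and is nowhere said to implement 11.3. Protocol 13.3.2 plans no table of special-interest or other significant AEs. This stands: a reader might infer that a protocol-specified analysis has been broken or that reporting is affected, and the documents support neither. What remains is a conflict of criterion on a shared topic. The two lists overlap on arrhythmia, AV block, bradycardia, syncope and loss of consciousness, and the SAP has no other table for them.

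- **Limited reach.** A reader might infer that the whole other significant TEAE row would be almost empty for young children whatever happened. It would not: AV block, other arrhythmias, syncope, hepatic and suicidality terms are counted without a heart-rate condition.

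- **Nothing is lost.** Every bradycardia TEAE stays in the general SOC and PT tables by age group, and in the serious, discontinuation and intensity tables where it qualifies. Low pulse and ECG rates are flagged against age-specific limits by visit, with listings. This also stands, and it limits the consequence to one classification.

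- **Low is not the same as marked.** The protocol gives no bpm value, and Table 8-2 is an ECG abnormality screen. Not every rate below an age limit is shown to be marked bradycardia, and in adolescents the 5 bpm gap is weak evidence of anything. In infants and toddlers, with gaps of 55 and 45 bpm, the argument loses its force: below 12 years the same limits stand in Table 8-1, which the SAP itself uses to define markedly abnormal values.

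**Conclusion.** The point holds as an inconsistency between current texts, confined to four preferred terms. For those terms the 45 bpm rule departs from the age-relative wording of Protocol 11.3 and lies 55, 45 and 15 bpm below the SAP's own low limits in the three youngest bands, with about 5 bpm in older subjects. Bradycardia AEs in infants and young children would almost never reach the other-significant-AE summaries.

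The words almost never are an inference from the ratios of 45% and 50% under 3 years, on the assumption that reported events seldom reach half the SAP's low limit. The documents give no heart-rate distribution and no expected bradycardia rate, so the number of events affected is unknown and may be zero. The study is descriptive, and neither primary safety variable is touched. Severity: should fix.

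**What to change.** Reconcile the Table 13-1 footnote with Protocol 11.3 by replacing the fixed 45 bpm with a pre-specified age-based classification rule for this table. One option is to use limits the SAP already defines: the low pulse limits of Table 8-1 (Vital Signs Abnormality Criteria) or the low heart-rate limits of Table 8-2 (Electrocardiogram Abnormality Criteria). If the sponsor considers that marked should mean something stricter than these, it can state another age-based rule.

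The SAP should name the chosen table by title, because the CBCL tables carry the same numbers. It should also say how subjects of 12 years and over are handled, where the two tables differ. Events under the four terms with no recorded heart rate should be kept in the table. This concerns tabulation only and leaves investigator reporting and subject management as they are.

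The cost is an edit to one footnote and a small programming change using limits already in the SAP. The downside is that a few more events may be listed. Because the study is open label, the rule should be set before events are reviewed for classification.

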## 13.2 Marked abnormality criteria for laboratory data

### 13.2.1 Marked abnormality criteria for hematology data

**Table 13-2: Hematology abnormality criteria**

Parameter	Age Range	Unit (conventional)	Abnormality criteria (conventional unit)	Unit (standard)	Abnormality criteria (standard unit)
Hematocrit	<2y	%	≤27 >45	%	≤27 >45
	2y - <17y	%	≤29 >47	%	≤29 >47
	≥17y	%	≤85% of LLN ≥115% of ULN	%	≤85% of LLN ≥115% of ULN
Hemoglobin	<2y	g/dL	≤9.0 >15.0	g/L	≤90 >150
	2y - <17y	g/dL	≤9.5 >16.0	g/L	≤95 >160
	≥17y	g/dL	≤85% of LLN ≥115% of ULN	g/L	≤85% of LLN ≥115% of ULN
WBC/ Leukocytes	All	10  /L	≤3.0 ≥16.0	G/L	≤3.0 ≥16.0
Lymphocytes Absolute	<2y	10  /L	<1.0 >9.8	G/L	<1.0 >9.8
	2y - <6y	10  /L	<0.7 >6.9	G/L	<0.7 >6.9

**Table 13–2: Hematology abnormality criteria**

Parameter	Age Range	Unit (conventional)	Abnormality criteria (conventional unit)	Unit (standard)	Abnormality criteria (standard unit)
	≥6y	10  /L	<0.6 >5.0	G/L	<0.6 >5.0
Basophils	>1m	%	≥5.0	%	≥5.0
Basophils Absolute	>1m	10  /L	≥0.4	G/L	≥0.4
Eosinophils	>1m	%	≥10	%	≥10
Eosinophils Absolute	>1m	10  /L	≥1.0	G/L	≥1.0
Monocytes	>1m	%	≥20.0	%	≥20.0
Monocytes Absolute	>1m	10  /L	≥2.0	G/L	≥2.0
Neutrophils Absolute	>1m	10  /L	<1.5	G/L	<1.5
Platelets	>1m	10  /L	≤100 ≥600	G/L	≤100 ≥600
RBC/ Erythrocytes	<2y	10  /L	<3.0	T/L	<3.0
	≥2y	10  /L	<3.5	T/L	<3.5

LLN=lower limit of normal, m=month, RBC=red blood cells, ULN=upper limit of normal, WBC=white blood cells, y=year.

A month is defined as 30 days; a year is defined as 365.25 days.

### 13.2.2 Marked abnormality criteria for chemistry data

**Table 13–3: Chemistry abnormality criteria**

Parameter	Age Range	Unit (conventional)	Abnormality criteria (conventional unit)	Unit (standard)	Abnormality criteria (standard unit)
AST (SGOT)	All	U/L	≥3.0 x ULN ≥5.0 x ULN ≥10.0 x ULN	U/L	≥3.0 x ULN ≥5.0 x ULN ≥10.0 x ULN
ALT (SGPT)	All	U/L	≥3.0 x ULN ≥5.0 x ULN ≥10.0 x ULN	U/L	≥3.0 x ULN ≥5.0 x ULN ≥10.0 x ULN

**Table 13–3: Chemistry abnormality criteria**

Parameter	Age Range	Unit (conventional)	Abnormality criteria (conventional unit)	Unit (standard)	Abnormality criteria (standard unit)
Alkaline Phosphatase	<4y	U/L	≥690	U/L	≥690
	4y - <10y	U/L	≥834	U/L	≥834
	10y - <17y	U/L	≥1761	U/L	≥1761
	≥17y	U/L	≥3.0 x ULN	U/L	≥3.0 x ULN
GGT	<6m	U/L	≥522	U/L	≥522
	6m - <1y	U/L	≥279	U/L	≥279
	1y - <13y	U/L	≥66	U/L	≥66
	13y - <17y	U/L	≥126	U/L	≥126
	≥17y	U/L	≥3.0 x ULN	U/L	≥3.0 x ULN
Total Bilirubin	>1m	mg/dL	≥2.0	umol/L	≥34.208
Total Protein	2m-<1y	g/dL	<3.0 ≥11.9	g/L	<30 ≥119
	1y - <17y	g/dL	<4.3 ≥12.0	g/L	<43 ≥120
	≥17y	g/dL	<4.3 ≥13.0	g/L	<43 ≥130
Albumin	<1y	g/dL	<1.6 ≥7.2	g/L	<16 ≥72
	≥1y - <17y	g/dL	<2.4 ≥8.4	g/L	<24 ≥84
	≥17y	g/dL	<2.6 ≥8.4	g/L	<26 ≥84
BUN	<1y	mg/dL	≥24	mmol/L	≥8.568
	1y - <17y	mg/dL	≥36	mmol/L	≥12.852
	≥17y	mg/dL	≥40	mmol/L	≥14.28
Creatinine	1y - <10y	mg/dL	>1.2	umol/L	>106.8
	10y - <16y	mg/dL	>1.8	umol/L	>159.12
	≥16y	mg/dL	≥2.0	umol/L	≥176.8

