6 SELECTION AND WITHDRAWAL OF SUBJECTS

6.1 Inclusion criteria

To be eligible to participate in this study, all of the following criteria must be met:

1. A signed informed consent has been obtained from the parent/legal representative and assent has been obtained from the subject (when possible or as required according to local Institutional Review Boards [IRBs]/Independent Ethics Committees [IECs]).
2. Subject and/or caregiver (which may be a parent, a legal representative, or other caregiver) are willing and able to comply with all study requirements including maintaining a daily seizure diary.
3. Subject is male or female, ≥1 month to <18 years of age. For preterm infants <1 year old, the corrected gestational age should be used when determining eligibility. The generally accepted definition of corrected gestational age, which is calculated by subtracting the number of weeks born before 37 weeks of gestation from the chronological age, will be used for this study.

4. Subject has a diagnosis of uncontrolled epilepsy with generalized seizures (Type II) according to the International Classification of Epileptic Seizures (1981) (see Section 17.1). The underlying epilepsy syndrome should be documented. Diagnosis should have been established by clinical history and an EEG with generalized spike-wave discharges. Documentation of the EEG finding of generalized spike waves (EEG recording or a report) is required. The EEG should have been performed no more than 18 months prior to Visit 1 (with no change to diagnosis or seizure types during this time).
5. Subject must have experienced 2 or more events (typical generalized seizures associated with diagnosed epilepsy syndrome) within the 6-week prospective Baseline Period.
6. Subject is on a stable dosage regimen of 1 to 3 AEDs. The daily dosage regimen of concomitant AED therapy must be kept constant for a period of at least 4 weeks prior to the Baseline Period.
7. Vagal nerve stimulation is allowed and will not be counted as a concomitant AED. The VNS device must be implanted for at least 6 months before Visit 1 and the device settings must be stable for at least 4 weeks before Visit 1 and be kept stable during the Baseline Period and the Treatment Period. Use of the VNS device magnet is allowed.
8. Body weight at Visit 1 is at least 4kg for infants.
9. Females of childbearing potential must have a negative pregnancy test at Visit 1.

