13.8 Determination of sample size

A total of 50 evaluable subjects are planned for enrollment for this study across 2 age groups. The first age group will consist of approximately 40 subjects between 4 years and <18 years of age. The second age group will consist of at least 10 subjects between 1 month and <4 years of age. Since the primary objective of this open-label exploratory study is to assess the safety and preliminary efficacy of LCM in subjects with generalized seizures and other epilepsy syndromes, a sample size of 50 evaluable subjects is deemed adequate for meeting the objectives of the study. No formal sample size calculations were performed.

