## 8.5 Clinical laboratory evaluations

The following laboratory parameters are measured within the study:

- Hematology: red blood cell count, white blood cell count, differential count (lymphocytes, basophils, eosinophils, monocytes, neutrophils), platelet count, hematocrit, and hemoglobin
- Chemistry: calcium, serum electrolytes (sodium, potassium, chloride, bicarbonate), total protein, albumin, phosphate, glucose, uric acid, alkaline phosphatase, urea nitrogen, creatinine, aspartate aminotransferase, alanine aminotransferase, gamma glutamyltransferase, total bilirubin, cholesterol, triglycerides
- Urinalysis: albumin, specific gravity, ketones, glucose, pH, microscopic exam for blood cells or casts/high power field
- Endocrinology: FSH, LH, T3, T4, TSH

Markedly abnormal laboratory values are defined in appendix 13.2. Treatment-emergent markedly abnormal (TEMA) values are defined as those markedly abnormal values which occur during the Treatment Period (including unscheduled visits), ie, with a normal Baseline value.

Observed values and changes from Baseline will be summarized for the parameters of hematology, chemistry and endocrinology given above. The Last Visit and minimum and maximum post-Baseline values during the Treatment Period will also be presented in these summaries. Repeated or unscheduled laboratory assessments during the study will not be presented in the by-visit summaries, but will be considered when determining the Last Visit, minimum post-Baseline value, and maximum post-Baseline value.

The number and percentage of subjects with a TEMA value, TEMA low value, and TEMA high value will be summarized by parameter and visit. Percentages will be based on the number of subjects with a nonmissing value at the respective visit. Additionally, a list of subjects with at least 1 TEMA value will be provided including all laboratory measurements of the respective parameter of the respective subject.

Urinalysis and pregnancy test results will only be listed.

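### SAP Table 13–3 has no creatinine or total cholesterol criterion for subjects under 1 year, yet those subjects stay in the denominator of the markedly-abnormal percentage

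*SAP*

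**What the plan says.** Protocol Section 6.1, criterion 3, sets eligibility as follows: "Subject is male or female, ≥1 month to <18 years of age". Protocol Section 13.8 plans the younger stratum: "The second age group will consist of at least 10 subjects between 1 month and <4 years of age".

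SAP Section 8.5 lists creatinine and cholesterol among the chemistry parameters and refers to Appendix 13.2 for what counts as markedly abnormal. Treatment-emergent markedly abnormal (TEMA) values are tabulated by parameter and visit, and "Percentages will be based on the number of subjects with a nonmissing value at the respective visit". SAP Section 3.2.5 applies the criteria by age at assessment. SAP Section 3.1 makes display by age group the default, with 1 month to under 4 years as the youngest column.

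In SAP Table 13–3 creatinine has three entries: "Creatinine 1y - <10y mg/dL >1.2 umol/L >106.8", then "10y - <16y mg/dL >1.8 umol/L >159.12", then "≥16y mg/dL ≥2.0 umol/L ≥176.8". Total cholesterol has one limit, for 1 year and over.

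**The concern.** The table defines a limit for part of the enrolled age range only, and the denominator rule makes no allowance for that. Protocol Amendment 4 was issued to open enrolment to subjects from 1 month to under 2 years, so infants are an intended part of the population.

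If the SAP is programmed as written, an infant with a creatinine result is counted as assessed and can never be counted as abnormal. A zero or low TEMA count in the youngest column would then be partly built in, and the table would not show it.

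The first creatinine row also pairs its two unit limits by a different factor from the other two rows, so the two unit columns are not the same rule.

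**Working it through.** **1. The stated standard-unit limit.** Inputs are the three creatinine rows of Table 13–3. The implied factor is the umol/L limit divided by the mg/dL limit.

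- 1 to <10 years: 106.8 / 1.2 = 89.0
- 10 to <16 years: 159.12 / 1.8 = 88.4
- 16 years and over: 176.8 / 2.0 = 88.4

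The plan's figure of 106.8 is not reproduced. With the factor of the other two rows, 1.2 × 88.4 = 106.08. The difference is 106.8 − 106.08 = 0.72 umol/L, and 0.72 / 106.08 = 0.68%. Converted back, 106.8 / 88.4 = 1.208 mg/dL. Rounding does not explain the gap, because the table carries two or more decimals in many other converted limits. Every other parameter with several converted rows uses one constant factor (for example BUN 0.357, calcium 0.25, phosphorus 0.323, uric acid 59.48).

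The two columns disagree only above 106.08 and up to 106.8 umol/L:

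- Whole umol/L: 106 fails both limits and 107 passes both, so no result is affected.
- Steps of 0.01 mg/dL: 1.20 fails both, and 1.21 × 88.4 = 106.96 passes both, so no result is affected.
- Steps of 0.1 umol/L (106.1 to 106.8) or 0.001 mg/dL (1.201 to 1.208): results can differ.

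**2. Age coverage.** Nine parameters in the same table have at least one band below 1 year: GGT, albumin, BUN, calcium, phosphorus, potassium, triglycerides, uric acid and T4. The BUN band reads "BUN <1y mg/dL ≥24 mmol/L ≥8.568". Several others apply to all ages or from 1 month. Creatinine and total cholesterol have nothing below 1 year. The gap does not look like a loss in text extraction: the last BUN row, "≥17y mg/dL ≥40 mmol/L ≥14.28", runs directly into the first creatinine row.

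**3. Effect on the TEMA percentage.** Let n be the subjects in a column with a value at a visit, k those under 1 year at that assessment, and e the number flagged.

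- Highest attainable rate: (n − k) / n
- Reported rate: e / n
- Rate among those who could be flagged: e / (n − k)

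The documents do not give k. Taking n = 10 for the youngest column as an illustration:

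- k = 0: no effect
- k = 1: maximum 9/10 = 90%; one flag is reported as 10.0%, against 1/9 = 11.1%
- k = 3: maximum 7/10 = 70%; 10.0% against 1/7 = 14.3%
- k = 5: maximum 5/10 = 50%; 10.0% against 1/5 = 20.0%

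In an overall column of 50, k = 3 gives a maximum of 47/50 = 94%. The direction needs no assumption: infants can add to the denominator and never to the numerator.

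**4. Subjects who turn 1 on treatment.** They become assessable from then on. TEMA also requires a normal Baseline, however, and for a Baseline taken under 1 year the table does not say what normal means.

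**The case against.** The strongest reply is that little is lost. SAP Section 8.5 still summarises observed creatinine, change from Baseline, Last Visit, and the minimum and maximum post-Baseline values, by default by age group. All data are listed, BUN has an infant limit, and an abnormal laboratory finding can be reported as an adverse event. All of that stands. A reader might infer that infant renal safety goes unreported. The documents do not support that: only the TEMA count, its percentage and the TEMA listing are affected. The study is exploratory and descriptive, and neither primary variable is touched.

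Three further readings are tempting and also fail.

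- **Total protein has the same gap because its row starts at 2 months.** TEMA values must fall in the Treatment Period. A subject is at least 30 days old at Visit 1, and Visit 2 follows 6 weeks ± 2 days later, so the age at first dose is at least about 30 + 40 = 70 days. The table's 2 months is 60 days. No on-treatment value falls below the row.
- **The youngest column's rate is multiplied by about 0.77.** With ages uniform over 1 month to <4 years, 10 × 11/47 = 2.3 of 10 would be infants, but that counts age at enrolment. By age at assessment, the same assumption leaves about 1.75 infants at Visit 6 (12 weeks after Visit 1) and 1.17 at Visit 9 (24 weeks), which gives about 0.82 and 0.88. The uniform spread, a total of exactly 10 and equal event rates are all unsupported.
- **The conversion slip is why infants are missed.** It sits in the 1 to <10 years row. The infant gap comes only from the absent band.

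**Conclusion.** The point holds in a narrow form. For creatinine and total cholesterol, a subject under 1 year at assessment is in the TEMA denominator with no chance of being flagged or listed. The percentage in the 1 month to <4 years column, and to a smaller extent overall, is therefore biased downward or at best unaffected. No single size can be given, because the number under 1 year at each visit is not in the documents. The illustrated maximum of 50% to 90% rests on n = 10 and an assumed k of 5 to 1.

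The 106.8 entry is an error by the table's own factor. It is 0.68% too high and has negligible effect at ordinary reporting precision. Both are worth correcting, and neither bears on the study's main conclusions.

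**What to change.** In SAP Table 13–3, take one of two routes for creatinine and total cholesterol below 1 year:

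- Add a sourced criterion, for example a multiple of the central laboratory's age-specific upper limit of normal, the form the table already uses for AST and ALT. The documents do not give that limit, so it must come from the laboratory.
- State that no criterion applies, exclude subjects under 1 year at assessment from that parameter's TEMA denominator, and footnote the table with the number excluded.

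Do not simply relabel the 1 to <10 years row to start at 1 month. Nothing in the documents supports 1.2 mg/dL for infants, and the table's own BUN limit is lower below 1 year (24 mg/dL) than from 1 to <17 years (36 mg/dL).

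State in SAP Section 8.5 how Baseline is judged normal when it was taken at an age with no criterion. Correct 106.8 to 106.08 umol/L.

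The cost is a table edit, a denominator condition in the programming and a footnote. No new data are needed.
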